## 7.0 TRIAL PROCEDURES

### 7.1 *Trial Procedures*

The Trial Flow Chart - **Section 6.0** summarizes the trial procedures to be performed at each visit. Individual trial procedures are described in detail below. It may be necessary to perform these procedures at unscheduled time points if deemed clinically necessary by the investigator.

Furthermore, additional evaluations/testing may be deemed necessary by the Sponsor for reasons related to subject safety. In these cases, such evaluations/testing will be performed in accordance with those regulations.

#### 7.1.1 *Administrative Procedures*

##### 7.1.1.1 *Informed Consent*

The Investigator must obtain documented consent from each potential subject prior to participating in a clinical trial. Copies of the informed consent form must be placed in the electronic medical record as well as study folder.

###### 7.1.1.1.1 *General Informed Consent*

Consent must be documented by the subject's dated signature or by the subject's legally acceptable representative's dated signature on a consent form along with the dated signature of the person conducting the consent discussion.

A copy of the signed and dated consent form should be given to the subject before participation in the trial.

The initial informed consent form, any subsequent revised written informed consent form and any written information provided to the subject must receive the IRB/ERC's approval/favorable opinion in advance of use. The subject or his/her legally acceptable representative should be informed in a timely manner if new information becomes available that may be relevant to the subject's willingness to continue participation in the trial. The communication of this information will be provided and documented via a revised consent form or addendum to the original consent form that captures the subject's dated signature or by the subject's legally acceptable representative's dated signature.

The informed consent will adhere to IRB/ERC requirements, applicable laws and regulations and Sponsor requirements.

###### 7.1.1.2 *Inclusion/Exclusion Criteria*

All inclusion and exclusion criteria will be reviewed by the physician-investigator to ensure that the subject qualifies for the trial.

###### 7.1.1.3 *Medical History*

A medical history will be obtained by the investigator or qualified designee. Medical history will include all active conditions, and any condition diagnosed within the prior 10 years that are considered to be clinically significant by the Investigator. Details regarding the disease

CONFIDENTIAL

This material is the property of the University of Pennsylvania. Do not disclose or use except as authorized in writing by the study sponsor.

for which the subject has enrolled in this study will be recorded separately and not listed as medical history.

#### **7.1.1.4 *Prior and Concomitant Medications Review***

##### **7.1.1.4.1 *Prior Medications***

The investigator or qualified designee will review prior medication use, including any protocol-specified washout requirement, and record prior medication taken by the subject within 28 days before starting the trial. Treatment for the disease for which the subject has enrolled in this study will be recorded separately and not listed as a prior medication.

##### **7.1.1.4.2 *Concomitant Medications***

The investigator or qualified designee will record medications, if any, taken by the subject during the trial.

#### **7.1.1.5 *Disease Details and Treatments***

##### **7.1.1.5.1 *Disease Details***

The investigator or qualified designee will obtain prior and current details regarding disease status.

##### **7.1.1.5.2 *Prior Treatment Details***

The investigator or qualified designee will review all prior cancer treatments including systemic treatments, radiation and surgeries.

##### **7.1.1.5.3 *Subsequent Anti-Cancer Therapy Status***

The investigator or qualified designee will review/document all new anti-neoplastic therapy initiated after the last dose of trial treatment.

#### **7.1.1.6 *Trial Compliance (Medication/Diet/Activity/Other)***

Please refer to [Table 3](#) for additional information on dose modification guidelines for itacitinib-related adverse events.

### **7.1.2 *Clinical Procedures/Assessments***

#### **7.1.2.1 *Adverse Event (AE) Monitoring***

The investigator or qualified designee will assess each subject to evaluate for potential new or worsening AEs as specified in the Trial Flow Chart and more frequently if clinically indicated. Adverse experiences will be graded and recorded throughout the study and during the follow-up period according to NCI CTCAE Version 5.0. Toxicities will be characterized in terms regarding seriousness, causality, toxicity grading, and action taken with regard to trial treatment. Please refer to [Section 10](#) for additional information on the assessment and recording of adverse events.

#### **7.1.2.2 *Full Physical Exam***

The investigator or licensed medical professional will perform a complete physical exam during the screening period. Clinically significant abnormal findings should be recorded as medical history. A full physical exam should be performed during screening,

CONFIDENTIAL

This material is the property of the University of Pennsylvania. Do not disclose or use except as authorized in writing by the study sponsor.

### **7.1.2.3 *Directed Physical Exam***

For cycles that do not require a full physical exam per the Trial Flow Chart, the investigator or qualified designee will perform a directed physical exam as clinically indicated prior to trial treatment administration. Directed physical examinations will be symptoms and disease driven based on physician discretion.

### **7.1.2.4 *Vital Signs***

The investigator or qualified designee will take vital signs at screening, prior to beginning each treatment cycle and at treatment discontinuation as specified in the Trial Flow Chart ([Section 6.0](#)). Vital signs should include temperature, pulse, weight and blood pressure. Height will be measured at screening only.

### **7.1.2.5 *Eastern Cooperative Oncology Group (ECOG) Performance Scale***

The investigator or qualified designee will assess ECOG status (see [Section 16.1](#)) as specified in the Trial Flow Chart.

### **7.1.2.6 *Tumor Imaging and Assessment of Disease***

The initial tumor imaging will be performed within 30 days prior to the first dose of trial treatment. Scans performed as part of routine clinical management are acceptable for use as the screening scan if they are of diagnostic quality and performed within 30 days prior to the first dose of trial treatment. A PET/CT may be used to fulfill baseline imaging requirements; however a PET/CT cannot be substituted for post-infusion imaging.

As responses to immunotherapy may be delayed, no subjects should have treatment decisions modified by the week 6 scan ( $42 \pm 7$  days) alone – this is intended as a research scan to guide biopsies. A repeat scan at 12 weeks (performed at the end of Cycle 4 prior to end of study visit) is intended for the primary outcome and clinical decision-making. Tumor imaging timing should follow calendar days and should not be adjusted for delays in cycle starts or extension of pembrolizumab cycle duration.

If a subject demonstrates radiographic progression at Week 12, repeat imaging may be performed at least 28 days later at the discretion of the treating investigator in order to confirm radiographic progression.

The same imaging techniques should be used to follow a subject throughout the trial. For subjects with brain metastases, MRI brain should be included in the imaging follow up prior to treatment and at any time when a subject develops new neurologic symptoms.

### **7.1.3 *Archived Tumor Tissue Sample***

If available, an archived tumor tissue sample will be requested for exploratory analysis after informed consent is obtained. Subjects will not be asked to undergo an additional procedure to obtain this sample.

### **7.1.4 *Unscheduled Research Sample Collections***

Beyond the research sample collections scheduled for specific time points, up to 30 mL (2 tablespoons) of additional peripheral blood may be drawn once per week to better characterize correlates of clinical events. In addition, samples obtained during procedures performed for standard clinical indications (e.g., clinical tumor biopsies, etc) may be diverted

CONFIDENTIAL

This material is the property of the University of Pennsylvania. Do not disclose or use except as authorized in writing by the study sponsor.

for research use if such diversion does not substantially increase the risk of the procedure or compromise standard clinical diagnostic studies.

#### **7.1.5 *Laboratory Procedures/Assessments***

Details regarding specific laboratory procedures/assessments to be performed in this trial are provided below in **Table 4**. The total amount of blood/tissue to be drawn/collected over the course of the trial (from pre-trial to post-trial visits), including approximate blood/tissue volumes drawn/collected by visit and by sample type per subject may vary depending upon clinical course of the subject and length of time on trial.

CONFIDENTIAL

This material is the property of the University of Pennsylvania. Do not disclose or use except as authorized in writing by the study sponsor.

**Table 4 Laboratory Tests**

Hematology	Chemistry	Other
Hematocrit	Albumin	Serum $\beta$ -human chorionic gonadotropin( $\beta$ -hCG)†
Hemoglobin	Alkaline phosphatase	Urine pregnancy test †
Platelet count	Alanine aminotransferase (ALT)	PT (INR)
WBC (total and differential)	Aspartate aminotransferase (AST)	aPTT
Red Blood Cell Count	Total protein	Total triiodothyronine (T3)
Absolute Neutrophil Count	Carbon Dioxide	Free tyroxine (T4)
	Blood Urea Nitrogen	Thyroid stimulating hormone (TSH)
	Calcium	
	Chloride	
	Creatinine	
	Glucose	
	Phosphorus	
	Potassium	
	Sodium	
	Magnesium	
	Total Bilirubin	
	Direct Bilirubin ( If total bilirubin is elevated above the upper limit of normal )	

† Performed on women of childbearing potential only. If urine pregnancy results cannot be confirmed as negative, a serum pregnancy test will be required.

After Cycle 1, pre-dose laboratory procedures can be conducted up to 72 hours prior to dosing. Results must be reviewed by the investigator or qualified designee and found to be acceptable prior to each dose of trial treatment.

### **7.1.6 Other Procedures**

#### **7.1.6.1 Withdrawal/Discontinuation**

When a subject prematurely discontinues from study treatment, all applicable activities scheduled for the End of Treatment Safety Follow-up Visit should be performed at the time of discontinuation. Any adverse events which are present at the time of discontinuation/withdrawal should be followed in accordance with the safety requirements outlined in **Section 10**. Subsequent to the End of Treatment Safety Follow-up Visits, subjects will be asked to return for an End of Study Visit as per the Trial Flow Chart in **Section 6.0**.

#### **7.1.6.2 Blinding/Unblinding**

Study treatment is open label for this study.

CONFIDENTIAL

This material is the property of the University of Pennsylvania. Do not disclose or use except as authorized in writing by the study sponsor.

### **7.1.7 Visit Requirements**

Visit requirements are outlined in **Section 6.0** - Trial Flow Chart. Specific procedure-related details are provided above in **Section 7.1** - Trial Procedures.

#### **7.1.7.1 Screening**

Visit requirements are outlined in **Section 6.0** - Trial Flow Chart. Specific procedure-related details are provided above in **Section 7.1** - Trial Procedures.

Prior to treatment initiation, potential subjects will be evaluated to determine that they fulfill the entry requirements as set forth in **Section 5.1**. Screening procedures may be repeated.

Written informed consent must be obtained prior to performing any tests/procedures for research purposes. Results of a test performed prior to the subject signing consent as part of routine clinical management are acceptable in lieu of a screening test if performed within the specified time frame.

#### **7.1.7.2 Treatment Period**

Visit requirements are outlined in **Section 6.0** - Trial Flow Chart. Specific procedure-related details are provided above in **Section 7.1** - Trial Procedures.

##### **7.1.7.2.1 End of Treatment Safety Follow-Up Visit**

The End of Treatment Safety Follow-Up Visit will occur at Week 12 (+/- 5d) in accordance with the Trial Flow Chart in **Section 6.0**. If the PI considers it beneficial for the subject, a fifth cycle may be administered prior to EOS visit. If a subject prematurely discontinues from study treatment, all applicable activities scheduled for the End of Treatment Safety Follow-up Visit should be performed at the time of discontinuation.

AEs will continue to be followed through the End of Treatment Safety Follow-Up Visit in accordance with the safety requirements outlined in Section 10. .

##### **7.1.7.3 End of Study Visit**

The End of Study Visit will occur at Week 16 (+/-10d). If the PI considers it beneficial for the subject, a fifth cycle may be administered prior to EOS visit. Subjects who remained on study treatment beyond Week 16 prior to the approval of Protocol Amendment V5, will be asked to undergo an End of Study Visit at their next clinic appointment prior to being withdrawn from the study.

Any SAEs experienced after this visit must be reported to the sponsor if the investigator suspects a causal relationship to the study treatment. Once an adverse event is detected, it should be followed until its resolution or until it is judged to be permanent.

### **7.1.8 Definition of an Overdose for This Protocol and Reporting of Overdose to the Sponsor**

#### **Pembrolizumab**

Please refer to package insert.

CONFIDENTIAL

This material is the property of the University of Pennsylvania. Do not disclose or use except as authorized in writing by the study sponsor.

## **Itacitinib**

For purposes of this trial, an overdose will be defined as any dose exceeding the prescribed dose of itacitinib. There is no clinical experience with overdosage of itacitinib. In clinical studies, the highest total daily dose was 1200mg and no adverse events were associated with this dose. Treatment of overdose will include supportive care.

All reports of overdose with and without an adverse event must be reported within 24 hours to the Sponsor.

## **8.0 STATISTICAL ANALYSIS PLAN**

### ***8.1 Statistical Design***

**3-stage optimal design.** The ORR for pembrolizumab in untreated PD-L1 positive advanced NSCLC was recently reported (Reck NEJM Oct 2016) to be 45% (95% CI 37-53%). The 3-stage optimal design (TT Chen, Statistics in Medicine 16:2701-2711,1997) tests the null hypothesis that the  $ORR \leq 35\%$  (clearly inferior to pembrolizumab) versus the alternative that the  $ORR \geq 55\%$  (clearly superior to pembrolizumab). Eleven evaluable subjects will be entered into the first stage of the study. If 2 or fewer of these 11 subjects respond, then the trial will be terminated. If at least 3 of these subjects respond, then an additional 19 evaluable subjects will be entered into the second stage of the study. If 12 or fewer of these 30 subjects respond, then the trial will be terminated. If at least 13 of these subjects respond, then an additional 18 evaluable subjects will be entered into the third stage of the study. If 20 or fewer of these 48 subjects respond, then it will be concluded that the regimen does not merit further investigation. If at least 21 of these 48 subjects respond, then it will be concluded that the regimen merits further investigation. If the true objective response rate is 35%, then the probability of recommending the regimen for further investigation (false positive error), is 0.100. While if the true objective response rate is 55%, then the probability of recommending the regimen for further investigation (power), is 0.906. If the true objective response rate is 35%, then the probability of early termination of the trial by the end of the second stage is 0.786. The software program, PASS v14 was employed to define this 3-stage design.

### ***8.2 Statistical Analysis Plan***

Based on evaluable subjects, the objective response rate and 95% confidence interval will be calculated. Duration of remission, progression-free survival and overall survival will be estimated by the method of Kaplan and Meier. Median values and 95% confidence intervals will be calculated. All observed toxicities will be graded and tabled. Toxicity tables will be separately constructed for cycles with pembrolizumab alone (cycles 1-2 and cycle  $\geq 5$ ) or pembrolizumab and itacitinib (cycles 3-4). Changes in immune pharmacodynamic biomarkers will be examined with scatter plots and summary statistics. Fold changes from baseline values will be estimated and summarized. **Sample Size:** The required sample size ranges from 11 to 48 evaluable subjects. In the event that 5% of subjects are not evaluable for objective response evaluation, the maximum sample size is 50 subjects. **Study Duration:** With an estimated accrual of 2 patients per month, it is anticipated that accrual will continue for approximately 24 months and subject follow-up will continue for up to year post Cycle 1/Day 1 (initiation of study treatment) for a total study duration of up to 36 months.

### **8.2.1 Hypothesis/Evaluation**

Study Objectives are stated in **Section 3.0**.

#### **Hypotheses**

- Pembrolizumab and itacitinib will be associated with an ORR of at least 55% among patients with previously untreated, PD-L1 positive metastatic NSCLC.
- Pembrolizumab and itacitinib will be well tolerated among patients with previously untreated, PD-L1 positive metastatic NSCLC.
- The addition of itacitinib to pembrolizumab will result in increased T cell activation in the peripheral blood and decreased interferon signaling in tumor tissue in the week 12 biopsy, compared to the week 6 biopsy.

#### **Analysis Endpoints**

##### **Primary**

There are two primary endpoints of this study: objective response rate (ORR) and tolerability of therapy.

##### **Objective response rate**

Objective response rate (ORR) is defined as the percentage of evaluable subjects who achieve a complete or partial clinical response according to RECIST criteria

##### **Tolerability of Therapy**

Tolerability of therapy will be determined on the basis of CTCAE adverse event reporting.

##### **Secondary**

##### **Immune biomarkers**

Priority assays for research blood collection will be multiparametric flow cytometry analysis of T cell subsets for changes in markers of exhaustion/activation. Additional assays include measurement of serum cytokines, circulating tumor cells and circulating DNA.

Tumor tissue will be analyzed by immunohistochemical, transcriptomic and genomic approaches.

##### **Overall Survival**

Overall Survival (OS) is defined as the time from initiation of study therapy to death due to any cause or last subject contact. Subjects without documented death at the time of the final analysis will be censored at the date of the last follow-up. Those patients who are currently on-study and progression-free at 16 weeks, will no longer be followed and will be censored for OS at week 16.

##### **Progression Free Survival (PFS)**

CONFIDENTIAL

This material is the property of the University of Pennsylvania. Do not disclose or use except as authorized in writing by the study sponsor.

Progression-free survival (PFS) is defined as days from initiation of study therapy to first documented disease progression, death due to any cause or last subject contact which documents progression-free status. Those patients who are currently on-study and progression-free at 16 weeks, will no longer be followed and will be censored for PFS at week 16.

#### Duration of response (DOR)

Duration of response (DOR) is defined as days from first documented complete or partial clinical response to first documented disease progression. Those patients who are currently on-study and progression-free at 16 weeks, will no longer be followed and will be censored for DOR at week 16.

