## 2.0 TRIAL DESIGN

### 2.1 *Trial Design*

This is an optimal 3-stage Phase II trial of pembrolizumab and itacitinib for first line treatment of PD-L1 positive metastatic NSCLC. Up to 48 evaluable subjects will be enrolled to examine the efficacy of adding itacitinib to pembrolizumab among patients with previously untreated metastatic NSCLC with tumor PD-L1 expression greater than or equal to 50%. Subjects will receive 2 cycles of pembrolizumab (200mg every 3 weeks), and then undergo repeat imaging and tumor biopsy. Beginning on the Day 1 of Cycle 3 the subject will receive itacitinib (selective JAK1 inhibitor) 200 mg daily for 6 weeks. Pembrolizumab will be continued at the same dose and frequency. After 6 weeks of treatment (week 12 of treatment overall) with itacitinib, repeat imaging and tumor biopsy will be performed. The scan is purely for biopsy planning, and no treatment decisions will be made based upon the results ([Figure 1](#)). Objective response by RECIST 1.1 will be determined based on the week 12 scan. Subjects who either experience documented progressive disease during the first 12 weeks of treatment or complete the first 12 weeks of treatment and undergo re-staging (i.e., PET/CT scan) will be considered evaluable for objective response evaluation. Subjects who are withdrawn from study (due to toxicity or other reasons) in the first 12 weeks of treatment and who do not undergo re-staging will be considered unevaluable for objective response evaluation but will be included in the safety analyses. These subjects will be replaced. Objective response rate (ORR) is defined as the proportion of evaluable subjects who achieve a complete or partial response according to RECIST 1.1 criteria.

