##### **4.2.3.1.2 Secondary**

Peripheral blood immune profiling will provide important mechanistic information on how PD-1 blockade and itacitinib function in human subjects. By studying treatment related changes in blood and tumor, and correlate these with response or resistance, superior and perhaps tailored combination treatment strategies could potentially be developed in the future. Correlative samples will be banked upon receipt and correlative assays performed in the following priority order.

High priority assays:

1. Multiparametric flow cytometry analysis of peripheral blood mononuclear cells to analyze T cell subsets and markers of functionality. T cell subsets will be determined using transcription factors and surface markers subsets. Functionality will be measured by examining activation markers, cytokines, effector molecules, and proliferation markers.
2. Transcriptomic analyses of tumor specimens to identify changes in gene expression after the addition of itacitinib to pembrolizumab. In particular, we will examine a subset of interferon-stimulated genes (ISGs) associated with resistance to checkpoint blockade in pre-clinical models.
3. Measurement of inflammatory cytokine or chemokine levels in subject serum. In particular, we will examine interferon levels and other cytokines regulated by the JAK1 pathway as biomarkers for both on-target drug activity and response.

Second priority assays:

1. Measurement of inflammatory cytokine or chemokine levels in subject serum. Circulating tumor cell (CTC) and circulating tumor DNA (ctDNA) measurements and profiling.

Additional secondary endpoints include progression free survival (PFS), overall survival (OS) and duration of response (DOR). PFS is defined as days from initiation of study therapy to first documented disease progression, death due to any cause or last subject contact which documents progression-free status. Those patients who are currently on-study and progression-free at 16 weeks, will no longer be followed and will be censored for PFS and OS at week 16. DOR is defined as the time from first documentation of partial or complete response to first documented disease progression. Those patients who are currently on-study and progression-free at 16 weeks, will no longer be followed and will be censored for PFS and OS at week 16.

CONFIDENTIAL

This material is the property of the University of Pennsylvania. Do not disclose or use except as authorized in writing by the study sponsor.

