### **8.2.2 Analysis Populations**

#### **8.2.2.1 Efficacy Analysis Populations**

Subjects who either experience documented progressive disease during the first 12 weeks of treatment or complete the first 12 weeks of treatment and undergo re-staging are considered evaluable for objective response evaluation. Subjects who are withdrawn from study (due to toxicity or other reasons) in the first 12 weeks of treatment and who do not undergo re-staging will be considered unevaluable for objective response evaluation but will be included in the safety analyses. The All Patients as Treated population will be used for estimation of PFS and OS.

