#### Secondary Objectives

1. Changes in immune pharmacodynamic biomarkers will be examined with scatter plots and summary statistics. Fold changes from baseline values will be estimated and summarized.
2. Duration of response, progression-free survival and overall survival will be estimated by the method of Kaplan and Meier. Median values and 95% confidence intervals will be calculated.

CONFIDENTIAL

This material is the property of the University of Pennsylvania. Do not disclose or use except as authorized in writing by the study sponsor.

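### Duration of response counts only documented progression as an event, so a responder's death without documented progression would be censored and would bias the estimate upward if it occurs

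*Combined protocol and SAP*

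**What the plan says.** DOR is defined twice, and neither definition mentions death.

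- Section 8.2.1, under Duration of response: "Duration of response (DOR) is defined as days from first documented complete or partial clinical response to first documented disease progression".
- Section 4.2.3.1.2: "DOR is defined as the time from first documentation of partial or complete response to first documented disease progression".

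PFS in Section 8.2.1 runs instead to "first documented disease progression, death due to any cause or last subject contact which documents progression-free status", so death from any cause is a PFS event.

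The only censoring rule for DOR is in Section 8.2.1. Subjects who are on study and progression-free at 16 weeks "will no longer be followed and will be censored for DOR at week 16". In Section 4.2.3.1.2 the sentence that follows the DOR definition gives the week-16 rule for PFS and OS and does not name DOR.

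For the analysis, Section 8.2.3 states: "Duration of response, progression-free survival and overall survival will be estimated by the method of Kaplan and Meier". Medians and 95% confidence intervals are planned.

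**The concern.** Death ends a response. Under the two DOR definitions, a responder who dies without documented progression has no DOR event, and the week-16 censoring rule does not reach a subject who died before week 16. A Kaplan-Meier analysis has only two states for an observation, event or censored, so this death would be censored. That treats the dead responder as having the same future risk of progression as the responders still alive. On the same date the same subject would be a PFS failure and, for DOR, a response still running when last seen.

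What is at stake is a favourable bias in a named secondary endpoint. The imaging schedule makes the omission more relevant than usual. The flow chart in Section 6.1 has no tumor imaging after the end of Cycle 4, and the repeat scan in Section 7.1.2.6 is discretionary and meant for subjects who show progression at week 12. A responder therefore has no scheduled scan between weeks 12 and 16 that could document progression, whereas a death would be known without imaging. Death could be a sizeable share of the few failures that can be observed, and it is the one left out.

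**Working it through.** **Is there a plan figure to reproduce?** Not for DOR: no median, event count or precision is stated. As a check that the primary design does not depend on this point, I enumerated the three-stage rule in Section 8.1 exactly by binomial (continue at 3 or more of 11, continue at 13 or more of 30, success at 21 or more of 48).

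| Quantity | Stated | Computed |
|---|---|---|
| False positive error at 35% | 0.100 | 0.0997 |
| Power at 55% | 0.906 | 0.9057 |
| Early termination by stage 2 at 35% | 0.786 | 0.7857 |

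All three match, and no DOR quantity enters them.

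**Direction.** Both codings of death use the same risk sets. With no tied times, at each death time the death-as-event curve is multiplied by 1 − (deaths / number at risk), and the death-censored curve is multiplied by 1. Hence S(event) = S(censored) × product of [1 − (deaths / number at risk)]. Censoring deaths can never lower the curve, and the two agree if there is no such death.

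**Observation window.** Section 2.1: "Objective response by RECIST 1.1 will be determined based on the week 12 scan". From week 12 to the week-16 cut-off is about 16 − 12 = 4 weeks. If a response could be dated from the week-6 scan, the window is about 16 − 6 = 10 weeks. The week-6 scan is described as being for biopsy planning, so 4 weeks is the more natural reading.

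**Number of responders.** Section 8.1: "If at least 21 of these 48 subjects respond, then it will be concluded that the regimen merits further investigation". I use 21 (21/48 = 44%) and 26 (0.55 × 48 = 26.4).

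**Illustration.** The counts of progressions and deaths are assumed. Deaths come before the progressions, and nobody else is censored before the last event.

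| Responders | Progressions | Deaths | Death censored | Death an event |
|---|---|---|---|---|
| 21 | 2 | 1 | 18/20 = 0.900 | 18/21 = 0.857 |
| 26 | 2 | 1 | 23/25 = 0.920 | 23/26 = 0.885 |
| 21 | 2 | 2 | 17/19 = 0.895 | 17/21 = 0.810 |
| 26 | 2 | 2 | 22/24 = 0.917 | 22/26 = 0.846 |

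In the first row the ratio is 20/21 = 0.952, and 0.900 × 0.952 = 0.857, as the formula requires. If the single death came after both progressions, the censored figure would be 19/21 = 0.905 and the other would stay at 0.857, so the order of events matters little.

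**Range under assumed rates.** Let P be the probability of progression and D the probability of death without documented progression, both within the window. With independent risks, S(censored) = 1 − P and S(event) = (1 − P)(1 − D), so the gap is (1 − P)D.

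- P = 20%, D = 1%: 0.80 × 0.01 = 0.008, or 0.8 percentage points.
- P = 5%, D = 5%: 0.95 × 0.05 = 0.0475, or about 4.8 percentage points.

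Expected deaths lost as events, if 2% to 5% of responders die in this way: 21 × 0.02 = 0.4 to 26 × 0.05 = 1.3. Neither the 1–5% nor the 5–20% range comes from the documents.

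**The case against.** The strongest reply is that little turns on this. DOR is descriptive, with no test, stopping rule or decision attached. It is observed for about 4 weeks in subjects just found to be responding, and its median is unlikely to be reached however death is coded. The deaths are not hidden: they count in PFS and OS, for which "The All Patients as Treated population will be used for estimation of PFS and OS", and toxicities are graded and tabled. The affected group may also be narrow. DOR ends at documented progression with no radiographic qualifier, and Section 10.2 recognises progression documented in the medical records. A cancer death with charted progression might therefore already be a DOR event. The main weakness of this endpoint is its truncated follow-up, which adding death does not cure.

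All of that stands as a limit on size. It does not make the definition right. A progression-only endpoint can be defended if death is handled as a competing risk, but the plan specifies Kaplan-Meier and says nothing of the kind.

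A reader might infer that the trial's DOR is overstated. The documents do not support that. The plan never says in words that deaths are censored (this follows from the event definition and the method), and nothing shows that any responder will die without documented progression. A reader might also infer that the conclusion on the regimen is at risk. It is not, because that conclusion depends on the response count alone.

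**Conclusion.** The point holds in conditional form. As defined, DOR would be biased upward if at least one responder dies without documented progression, and unbiased on this account if none does. The direction is certain and the size is not. One such death among 21 responders with 2 progressions moves the week-16 estimate from 0.857 to 0.900. Across the assumed rates the shift is roughly 1 to 5 percentage points. These figures rest on assumed event counts or rates, on the week-16 cut-off, and in the rate-based range on independence of death and progression. This is a minor correction to a secondary endpoint. It is best settled in advance, because with so few possible events one death visibly moves the curve, and its status should not be decided after it is seen.

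**What to change.** In Sections 8.2.1 and 4.2.3.1.2, define DOR as the time from first documented complete or partial response to first documented progression or death from any cause, whichever comes first. Censor all other responders at the last contact or assessment that documents progression-free status, no later than week 16.

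A bare rule that censors everyone else at week 16 should be avoided. A responder lost at week 13 would be credited with three weeks (16 − 13) that were never observed, and the rule would not match the last-contact wording of PFS.

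In Section 4.2.3.1.2, also correct the sentence after the DOR definition so that it gives the censoring rule for DOR, as Section 8.2.1 does.

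The cost is a phrase and a censoring sentence in two places. Deaths are already needed for PFS and OS, so no new data are required. The only downside is a possibly shorter reported DOR.
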